3.1.2 Dose Escalation Common Rules

Starting dose of SX-682 will be 25 mg by mouth twice daily (50 mg total daily dose).

The first 3 participants enrolled on a given dose level of Arms 1 and 2 will be observed for DLT. If no DLT in those 3 participants, the next dose level will open. If DLT(s) occur, see **Table 5**.

There will be an interval of at least 28 days between enrolling the last participant on a given dose level and enrolling a participant on the next dose level in Arms 1 and 2, in order to assess for DLTs.

Subjects who do not complete the DLT observation period for reasons other than a DLT will be replaced and not included in the evaluation.

Participants will be eligible for the DLT evaluation if at least ≥ 85 percent of SX-682 scheduled doses were taken and 100% of scheduled doses of M7824 or CV301 were administered within the DLT period.

In case of DLT, DLT will be documented and participant, per PI discretion, may continue study treatment if toxicity could be managed by interruption of the dose of study treatment or dose reductions (See section **3.4**). Participant, once having DLT, will not be used for DLT evaluation on another dose level if treated on a lower dose level.

Any of the trial drugs may be discontinued for toxicity per the discretion of the primary investigator if it is felt that the toxicity can be directly linked to a specific drug or drugs. Per PI

discretion participant can continue treatment with 2 other drugs. However, if 2 drugs or more must be discontinued, the participant will be taken off treatment.

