3.1.1 Dose Limiting Toxicity

Dose-limiting toxicity (DLT) will be defined as any one of the following adverse events (AEs), as defined by CTCAE v5.0, possibly attributable to study drugs by the Investigator, that occur within 28 days after the start of study therapy:

- Any Grade 4 AEs, except for:
 - laboratory values that are determined to not be clinically significant or single laboratory valued that resolve to Grade ≤ 1 or baseline grade within 7 days with adequate medical management.
 - adverse drug reaction which in the opinion of the investigator is not clinically relevant or can be medically managed with minimal risk to the participant (e.g. placement of a pleural catheter for recurrent inflammatory pleural effusions)
- Average QTcf ≥ 501 msec or > 60 msec change from baseline (Grade 3)
- Any Grade 3 AEs except for any of the following:
 - Grade 3 flu-like symptoms or fever, as well as associated symptoms of fatigue, headaches, nausea, emesis which can be controlled with conservative medical management.
 - Tumor flare phenomenon defined as local pain, irritation, or rash localized at sites of known or suspected tumor.

- Any Grade ≥ 3 drug-related amylase or lipase abnormality that is not associated with symptoms or clinical manifestations of pancreatitis.
- Grade 3 Hgb decrease (< 8.0 g/dL) that is clinically manageable with blood transfusions or erythroid growth factor use does not require treatment discontinuation.
- Keratoacanthoma and squamous cell carcinoma of the skin.
- Any endocrinopathy that can be medically managed with hormone replacement
- Grade 3 neutropenia without fever
- Since the safety profile of M7824 is well characterized (see IB), a single grade 3 adverse event known to be associated with M7824, as per IB section 6.2.6 will not be considered a DLT.
 - Additionally, M7824 has a known potential to cause bleeding, with a rate of grade 3 bleeding events as high as 15.3% [92]. Therefore a grade 3 bleeding event will not be considered a DLT.
- Any grade 3 adverse drug reaction which in the opinion of the investigator is not clinically relevant or can be medically managed with minimal risk to the participant (e.g. placement of a pleural catheter for recurrent inflammatory pleural effusions)
- Any grade 3 or higher adverse event or unexpected toxicities due to the combination of therapies that would not be expected with individual agents alone, will be considered a DLT.

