3.4.3 CV301

Dose delays or dose omissions of CV301 vaccines are allowed per PI discretion. There are no dose reductions for the CV301 vaccines.

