3.4.4 M7824

Dose delays or dose omissions of M7824 are allowed per PI discretion. There are no dose reductions for M7824.

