10.3.1 Evaluable for toxicity

All participants will be evaluable for toxicity from the time of their first treatment with SX-682. Participant will be eligible for the DLT evaluation if at least ≥ 85 percent of SX-682 scheduled doses were taken and 100% of scheduled doses of M7824 or CV301 were administered within the DLT period.

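### The DLT-evaluability rule joins M7824 and CV301 with *or*, so read literally a DLT-free participant who missed one of them still counts toward clearing a dose level of a regimen that contains both

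*Combined protocol and SAP*

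**What the plan says.** Section 3.1.2 sets the exposure needed for DLT evaluation: "at least ≥ 85 percent of SX-682 scheduled doses were taken and 100% of scheduled doses" of the other two drugs, the second condition being "100% of scheduled doses of M7824 or CV301 were administered within the DLT period". Section 10.3.1, in the statistical chapter, repeats it: "100% of scheduled doses of M7824 or CV301 were administered within the DLT" window.

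The surrounding rules are:

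- **Window (3.1.1).** DLTs are events "that occur within 28 days after the start of study therapy".
- **Escalation (3.1.2 and Table 5).** "If no DLT in those 3 participants, the next dose level will open".
- **Replacement (3.1.2).** "Subjects who do not complete the DLT observation period for reasons other than a DLT will be replaced and not included in the evaluation".
- **Omissions (3.4.4 and 3.4.3).** "Dose delays or dose omissions of M7824 are allowed per PI discretion"; "Dose delays or dose omissions of CV301 vaccines are allowed per PI discretion". Neither section makes an exception for the DLT period.

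The primary objectives (1.1.1) and the descriptions of Arms 1 and 2 (3.1.3, 3.1.4) concern SX-682 followed by, or given with, both M7824 and CV301.

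**The concern.** The evaluability rule decides who may stand as evidence that a dose level is tolerable, and each decision rests on 3 to 6 participants. The sentence uses *and* to attach the SX-682 condition and *or* between the other two drugs. On the literal reading, a participant who missed every M7824 dose in the window, or every CV301 dose, passes the exposure test if the other drug was given in full.

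Such a participant cannot show toxicity that needs the missing drug. That includes the grade 3 or higher events caused by the combination, which 3.1.1 lists separately as DLTs. Counting the participant as DLT-free would bias the observed DLT rate for the full regimen downward. The dose chosen in Arm 2 is then carried into both Arm 3 cohorts.

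**Working it through.** **1. The rule as logic.** Take a participant without a DLT, with at least 85% of SX-682 doses taken and 28 days of observation completed.

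| M7824 in window | CV301 in window | Evaluable, *or* read literally | Evaluable if both required |
|---|---|---|---|
| full | full | yes | yes |
| none | full | yes | no |
| full | none | yes | no |
| not full | not full | no | no |

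The two readings disagree on the middle rows, and the gap is symmetric in the two drugs.

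**2. Can the middle rows occur?** Yes, under the protocol's own rules. Either drug may be omitted at the PI's discretion (3.4.3, 3.4.4). A dose outside its visit window is skipped and not made up (3.3.1). A delay of one drug does not delay the others (3.4.1). One drug may be stopped for toxicity while the other two continue (3.1.2).

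**3. Does another rule remove such a participant?** No. The replacement rule covers those who do not complete the observation period. Someone followed for 28 days with a missed infusion has completed it.

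**4. How much exposure is one missed visit?** Therapy starts on Day -14L. C1D1 falls 14 days later and C1D15 falls 28 days later, on the boundary of the window. So one M7824 visit lies in the window, or two if the boundary day counts. One omitted infusion can mean no M7824 exposure.

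**5. Illustrative size.** The documents state no DLT risks and no operating characteristics for the 3+3 design, so there is no figure to reproduce and the risks below are assumptions. Let p be the DLT risk on the full regimen and q the risk for one of the first three participants who lacked M7824. Any second group of three is fully dosed.

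- P(0 of 3) = (1−q)(1−p)²
- P(1 of 3) = q(1−p)² + (1−q)·2p(1−p)
- P(clear) = P(0 of 3) + P(1 of 3)·(1−p)³

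With p = 0.30: (1−p)² = 0.49, 2p(1−p) = 0.42 and (1−p)³ = 0.343.

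| q | P(0 of 3) | P(1 of 3) | P(clear) |
|---|---|---|---|
| 0.30 (all fully dosed) | 0.343 | 0.441 | 0.343 + 0.441×0.343 = 0.494 |
| 0.25 (M7824 adds 5 points) | 0.3675 | 0.4375 | 0.518 |
| 0.20 (M7824 adds 10 points) | 0.392 | 0.434 | 0.541 |
| 0.10 | 0.441 | 0.427 | 0.587 |
| 0.05 | 0.4655 | 0.4235 | 0.611 |

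With q = 0.10 and other values of p, P(clear) moves from 0.709 to 0.756 at p = 0.20, and from 0.309 to 0.425 at p = 0.40.

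**6. At a level with six participants.** Table 5 and 3.1.5 require six at the RP2D. With one of the six lacking M7824:

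P(at most 1 DLT in 6) = (1−q)[(1−p)⁵ + 5p(1−p)⁴] + q(1−p)⁵

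At p = 0.30 this is (1−q)×0.528 + q×0.168. It gives 0.420 with all six fully dosed, 0.438 and 0.456 at q = 0.25 and 0.20, and 0.492 and 0.510 at q = 0.10 and 0.05.

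**The case against.** **The word can be read the other way.** A requirement for all scheduled doses of M7824 or CV301 can mean that no dose of either drug was missed, which requires both. The objectives and arm descriptions name both drugs and favour that reading. A reader might infer that the plan in fact admits participants who never received M7824. The documents do not show that; they show a sentence with two readings that classify the same person differently. This part of the objection stands and sets how strongly the point can be put. It does not remove the defect, because the rule gates escalation and nothing else in the protocol settles the meaning.

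**M7824 may contribute little to DLT risk.** Section 3.1.1 excludes a single grade 3 event known to be associated with M7824, and also excludes grade 3 bleeding. M7824 is given at a fixed dose while SX-682 is escalated. The first 14 of the 28 days are lead-in without M7824 for everyone. All of this makes the 5–10 point contribution at least as plausible as the larger one. In the other direction, grade 4 events in general and toxicities of the combination remain DLTs.

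**The RP2D is better protected than the first-cohort figures suggest.** With six participants the shift is smaller (working, step 6). All these figures are also conditional on an omission occurring, and the documents give no frequency for that.

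**Changing *or* to *and* is not enough.** A reader might infer that one word settles it. It does not, for two reasons. The sentence has no exception for participants with a DLT. Someone given CV301 but not M7824 who then has a DLT is evaluable under *or* and would not be under *and*, so the bare swap could drop DLTs from the count. Nor does the swap trigger replacement, which depends on completing the observation period and not on doses received.

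**Conclusion.** The point holds as a wording defect in a rule that gates dose escalation. Read literally, the rule in 3.1.2 and 10.3.1 lets a DLT-free participant who missed all M7824, or all CV301, in the 28-day window count toward clearing a dose level. The protocol's own rules allow that record to arise, and no section excludes it. The intent is probably that both drugs are required.

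The size cannot be derived from the documents. With an assumed 30% full-regimen risk and one of the first three lacking M7824, the chance of clearing the level rises by 2 to 5 points if M7824 contributes 5–10 points of that risk. It rises by 9 to 12 points if the risk without M7824 is only 5–10%. A reader might take the larger figures as the expected bias in the RP2D. The documents do not support that, since those figures describe a single first cohort, assume that M7824 causes most of the DLTs, and take the omission as given.

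**What to change.** In both 3.1.2 and 10.3.1, replace the evaluability sentence with a rule that separates participants by outcome:

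- A participant without a DLT is evaluable only if at least 85% of scheduled SX-682 doses, and all scheduled doses of both M7824 and CV301, were given within the DLT period.
- A participant without a DLT who does not meet this is replaced, even if observed for the full 28 days.
- A participant who has a DLT in the period is evaluable whatever doses were received.

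The text should also say whether the C1D15 doses, which fall on day 28 after the first dose, count as scheduled within the period.

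No dose or treatment rule changes. The cost is an occasional replacement participant. Section 10.2 allows 105 treated participants against at most 60 + 21 + 16 = 97 evaluable. That leaves 8 places, which must also cover inevaluable participants in Arm 3.

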3.1.3 Sequential Dose Escalation (Arm 1)

In Arm 1 participants will receive SX-682 as monotherapy for 2 weeks during the lead-in (Days -14L to -1L) and then continue treatment with M7824 and CV301 starting Cycle 1, Day 1.

The dose escalation will start from dose level 1 and continue until dose level 3 (**Table 4**) in sequential order using a standard 3+3 design (**Table 5**). Aside from looking at DLTs within a given dose level, the total number of DLTs will also be evaluated among the initial 3DLs in Arm 1 to guide further safety assessments. If there are 0 DLTs reported in the initial 3 DLs (minimum of 12 participants) in Arm 1, then Arm 2 can open as depicted in Schema 2 with starting at DL2. If there is 1 or more DLTs identified among all the participants in the first 3 DLs, enrollment in Arm 1 will continue with the next participants being enrolled on DL4 then DL5, using a 3+3 design in order to determine the maximally tolerated dose (MTD) before proceeding to Arm 2, DL 1.

Dose escalation will proceed in groups of 3–6 participants. The MTD is the dose level at which no more than 1 of up to 6 participants experience DLT during 28 days of treatment, and the dose below that at which at least 2 (of ≤ 6) participants have DLT as a result of the drug.

Table 4: Dose levels of SX-682

Dose Escalation Schedule		
Dose Level	Dose of SX-682	Total SX-682 daily dose
Level 1	25 mg by mouth twice daily	50 mg
Level 2	50 mg by mouth twice daily	100 mg
Level 3	100 mg by mouth twice daily	200 mg
Level 4	200 mg by mouth twice daily	400 mg
Level 5	400 mg by mouth twice daily	800 mg

SX-682 is dispensed as a 25mg tablet. M7824 and CV301 will be given at fixed doses.

Table 5. Escalation Decision Rules

Number of Participants with DLT at a Given Dose Level	Escalation Decision Rule*
0 out of 3	Enter up to 3 participants at the next dose level
≥ 2	Dose escalation will be stopped. This dose level will be declared the maximally administered dose (highest dose administered). Up to three (3) additional participants will be entered at the next lowest dose level if only 3 participants were treated previously at that dose.
1 out of 3	Enter up to 3 more participants at this dose level. 
• If 0 of these 3 participants experience DLT, proceed to the next dose level.• If 1 or more of this group suffer DLT, then dose escalation is stopped, and this dose is declared the maximally administered dose. Up to three (3) additional participants will be entered at the next lowest dose level if only 3 participants were treated previously at that dose.
≤ 1 out of 6 at highest dose level below the maximally administered dose	This is the MTD and is generally the recommended phase 2 dose. At least 6 participants must be entered at the recommended phase 2 dose.

3.1.4 Combination Dose Escalation (Arm 2)

In Arm 2 participants will receive SX-682 as monotherapy for the lead-in (Days -14L to -1L) and then will continue treatment with SX-682 combined with M7824 and CV301 starting on Cycle 1 Day 1.

If 6 participants have been treated in Arm 1 at dose level 3 without DLT during DLT period, the dose escalation of SX-682 will start from dose level 2 and continue until dose level 5 ([Table 4](#)) in sequential order using a standard 3+3 design ([Table 5](#)).

If there was 1 or more DLT in Arm 1 at dose level 1 through 3 during DLT period, the dose escalation of SX-682 will start from dose level 1 and continue until dose level 5 ([Table 4](#)) in sequential order using a standard 3+3 design ([Table 5](#)).

If in Arm 1 dose level 1 or 2 are estimated as MTD, we will submit an amendment with justification for study continuation.

[figure not shown]
Dose escalation will proceed in groups of 3–6 participants. The MTD is the dose level at which no more than 1 of up to 6 participants experience DLT during 28 days of treatment, and the dose below that at which at least 2 (of ≤ 6) participants have DLT as a result of the drug. The RP2D may not necessarily be the same as the MTD.

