3.1.5 Expansion Cohorts (Arm 3, Cohorts 2 and 3)

The safety, tolerability and efficacy evaluation of combination will continue with the RP2D of SX-682, M7824 and CV301 found during the dose escalation cohort (Arms 1 and 2). The dose of SX-682 used in combination with M7824 and CV301 in Arm 3 cannot exceed the highest tolerable dose for SX-682 monotherapy as determined in Arms 1 and 2.

Enrollment into the expansion cohorts can commence after the RP2D has been determined (after the 6th participant on relevant dose level completes the DLT evaluation period). For performance of the expansion cohorts, see **Schema 3**

Schema 3 Expansion Cohorts in Triple Negative Breast Cancer and HPV negative HNSCC

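### The amendment clause in 3.1.4 covers an Arm 1 MTD at dose level 1 or 2, but not the worse case in which dose level 1 itself is not tolerated

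*Combined protocol and SAP*

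**What the plan says.** Section 3.1.4 sets the Arm 2 starting level from the Arm 1 result. With six participants at DL3 and no DLT, Arm 2 starts at DL2. The alternative condition is "If there was 1 or more DLT in Arm 1 at dose level 1 through 3 during DLT period", and then Arm 2 starts at DL1. A third sentence provides the brake: "If in Arm 1 dose level 1 or 2 are estimated as MTD, we will submit an amendment with justification for study continuation".

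The MTD is defined identically in 3.1.3 and 3.1.4: "The MTD is the dose level at which no more than 1 of up to 6 participants experience DLT during 28 days of treatment", and it lies one step below a level with at least two DLTs. Under Table 5, two or more DLTs at a level stop escalation, and then "Up to three (3) additional participants will be entered at the next lowest dose level" if only three were treated there. Table 4 begins at DL1 (25 mg twice daily), which is also the starting dose in 3.1.2.

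Section 3.1.3 says that after one or more DLTs in the first three levels, Arm 1 goes on to DL4 and DL5 by 3+3 "in order to determine the maximally tolerated dose (MTD) before proceeding to Arm 2, DL 1".

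The regimens differ after the lead-in. Arm 1 stops SX-682 there. Arm 2 does not: "In Arm 2 participants will receive SX-682 as monotherapy for the lead-in (Days -14L to -1L) and then will continue treatment with SX-682". It then runs alongside the other two agents.

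**The concern.** The clause requires an amendment when DL1 is tolerated well enough to be the MTD. It does not mention the worse result, in which DL1 is not tolerated. In that case the only 3.1.4 sentence whose condition is met is the one that starts Arm 2 at DL1.

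Arm 2 DL1 contains everything in Arm 1 DL1 (the same 14-day lead-in at 50 mg a day and the same M7824 and CV301 schedule) and adds SX-682 after the lead-in. A stop at DL1 need not be due to SX-682, because DLTs are events "possibly attributable to study drugs by the Investigator, that occur within 28 days after the start of study therapy", and that window also takes in the start of M7824 and CV301. Whichever drug was responsible, Arm 2 DL1 gives at least as much of it. An amendment would bring IRB review and approval first (Statement of Compliance). As worded, 3.1.4 does not call for that step in the case that needs it most.

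**Working it through.** **Plan's own counts.** Section 10.2 gives Arm 1 a range of 9 to 30 participants: 3 levels × 3 = 9 and 5 levels × 6 = 30. A direct stop at DL1 treats only 3 or 6 people, below that minimum, so 10.2 does not describe this path.

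**Every DL1 result in the first cohorts, against the rules.**

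| DL1 result | Table 5 | Can DL1 be the MTD? | Amendment clause | Condition for Arm 2 start at DL1 |
|---|---|---|---|---|
| 0/3 | escalate | yes | depends on higher levels | depends on DL2 and DL3 |
| 1/6 | escalate | yes | depends on higher levels | met |
| 2/3, 3/3 | stop | no | not triggered | met |
| 2/6, 3/6, 4/6 | stop | no | not triggered | met |

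All five stopping results leave no MTD. The same happens if DL1 passes at 0/3, DL2 stops, and the DL1 backfill then brings two or more DLTs.

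**Dose in the 28-day window at DL1.** Arm 1: 14 days × 50 mg = 700 mg of SX-682. Arm 2: 28 days × 50 mg = 1,400 mg.

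**What a DL1 stop shows.** The observed DLT rate is at least 2/6 = 33%. The exact 95% interval is 4% to 78% for 2/6 and 9% to 99% for 2/3, so the evidence is thin, but it is all there would be. Arm 2 DL1 would expose 3 to 6 more participants.

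**How often the case arises.** The documents give no DLT rates, so those below are assumptions. For true rate p, the chance that a level stops is s(p) = 1 − (1−p)³ − 3p(1−p)⁵.

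- s(0.05) = 1 − 0.8574 − 0.1161 = 0.027
- s(0.10) = 1 − 0.7290 − 0.1771 = 0.094
- s(0.20) = 1 − 0.5120 − 0.1966 = 0.291

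Failed backfill adds two routes, with f(p) = 1 − (1−p)³ − 3p(1−p)² for two or more DLTs among three added participants:

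- DL2 stops and DL1 fails: (1−p₁)³ s(p₂) f(p₁)
- DL3 stops and DL2 and DL1 both fail: (1−p₁)³ (1−p₂)³ s(p₃) f(p₂) f(p₁)

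Totals:

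- DL1 to DL3 rates of 5/10/15%: 0.0266 + 0.0006 + 0.0000 = 2.7%
- DL1 to DL3 rates of 10/20/30%: 0.0939 + 0.0060 + 0.0006 = 10.0%

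**If Arm 2 did open.** With an assumed true rate of one third, Arm 2 DL1 would itself stop with probability s(1/3) = 1 − 0.2963 − 0.1317 = 57%.

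**The case against.** The strongest reply is that 3.1.4 sets a starting dose, while 3.1.3 sets when Arm 2 opens. Section 3.1.3 gives two routes: no DLTs, or more Arm 1 escalation so that the MTD is known first. After a DL1 stop neither is completed, so Arm 2 would stay closed. This is a fair reading, and it is why a reader who infers that the plan simply sends participants into Arm 2 goes too far. But the MTD phrase states the purpose of continuing to DL4 and DL5, 3.1.4 does not repeat it, and no visible text says that Arm 2 stays closed when there is no MTD.

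The second reply is that other safeguards would act. In 3.2, two grade 3 DLTs meet neither count-based trigger (one grade 5 or two grade 4 events). The third trigger, grade 3 or worse toxicity beyond the expected rate for the individual agents, could well be met, since the DLT definition already excludes many known or manageable events. That would halt enrollment, require a report to FDA and convene the DSMB (7.5.2). Section 7.5.1 bases dose decisions on earlier toxicity, and 13.1 allows suspension for unacceptable risk. All of this stands as protection. However, the third trigger has no number, the 3.2 halt is temporary, and none of these sections says what becomes of Arm 2. The ceiling in 3.1.5 does not help either: "The dose of SX-682 used in combination with M7824 and CV301 in Arm 3 cannot exceed the highest tolerable dose for SX-682 monotherapy" is written for Arm 3.

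Third, Schemas 1 and 2, the figure after the clause and any footnote to Table 5 are not visible in the text reviewed and may settle the matter. That limits confidence.

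A reader might also infer that 3.1.3 sends Arm 1 on to DL4 after a failed lower level, because its condition has no upper limit. The documents do not support that: the sentence itself invokes 3+3, and Table 5 and 10.2 stop escalation at two or more DLTs.

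**Conclusion.** The point holds as a gap in 3.1.4 and, at best, a conflict with 3.1.3 on a safety decision. It does not show that Arm 2 would open unreviewed. Intent is fairly clear: a sponsor that wants an amendment when DL1 is the MTD would presumably want one when DL1 is not tolerated.

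Severity is low. The case arises about 3% to 10% of the time if the true DL1 rate is 5% to 10% and the higher levels follow the assumed patterns. It would be more frequent at higher rates: 29% for a direct DL1 stop at a 20% rate. These figures say how often the rule would be needed, not how often harm would follow. The logical finding needs no assumed rate. It rests on the MTD definition, the absence of a level below DL1, and the visible text.

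**What to change.** In 3.1.4, replace the amendment clause with:

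> If Arm 1 stops at dose level 1 (on escalation or on backfill), or if dose level 1 or 2 is estimated as the MTD, Arm 2 will not open until an amendment with justification is approved.

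Leave the sentence on one or more DLTs as it is, so that Arm 2 can still start at DL1 after an Arm 1 stop at DL4 or DL5. If the schemas show Arm 2 opening after a DL1 stop, align them. Section 3.1.3 needs no change for this point.

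The cost is one sentence. No participants are added, and the maxima of 18 in the first three levels, 30 per arm and 60 in phase I are unchanged. In the uncommon case covered, Arm 2 waits for approval.
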